5.1 INCLUSION CRITERIA

To be eligible to participate in the study, an individual must meet all of the following criteria:

1. Be 50 years or older
2. Have a diagnosis of prodromal or mild-to-moderate AD supported by AD biomarkers (e.g., CSF, amyloid PET or plasma biomarkers)
3. Have a MMSE score between 14 and 30
4. Be fluent in English
5. Have a reliable study partner who will agree to accompany the subject to study visits and spend the necessary time to learn how to use, control, and maintain the Vielight Neuro Gamma device, how to administer tPBM treatments, and how to log its use during the 16 weeks of the study
6. Agree to under two lumbar punctures, approximately 16 weeks apart.

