8 STUDY ASSESSMENTS AND PROCEDURES

8.1 ENDPOINT AND OTHER NON-SAFETY ASSESSMENTS

Cognitive and Behavioral Outcome Measures will be assessed at baseline and after 16 weeks by a study staff member who will be blind to treatment assignment. The measures are standard in the field and have well-established validity and reliability:

- The **Mini-Mental State Exam (MMSE)** (Folstein et al., 1975) is a fully structured screening instrument frequently used for Alzheimer’s disease drug studies. The scale evaluates orientation, memory, attention, concentration, naming, repetition, comprehension, and ability to create a sentence and to copy two overlapping pentagons.
- The **Alzheimer’s Disease Assessment Scale, Cognitive Subscale (ADAS-cog)** (Rosen et al., 1984) is a structured scale that evaluates memory (word recall, word recognition), reasoning (following commands), language (naming, comprehension), orientation, ideational praxis (placing letter in envelope) and constructional praxis (copying geometric designs). Ratings of spoken language, language comprehension, word finding difficulty, and ability to remember test instructions are also obtained. The test is scored in terms of errors, with higher scores reflecting poorer performance. Scores can range from 0 (best) to 70 (worse).
- The **Color Trails Test (CTT)** (D’Elia et al., 1996) is a non-verbal test of visual attention, graphomotor sequencing, and effortful executive processing abilities (i.e., sustained attention and set shifting).
- The **Neuropsychiatry Inventory (NPI)** (Cummings, 1997) is a well-validated, reliable, multi-item instrument to assess psychopathology in AD based on an interview with a study companion or qualified partner.
- The **Alzheimer’s Disease Cooperative Study, Activities of Daily Living (ADCS-ADL)** (Galasko et al., 1997) assesses the competence of patients with AD in basic and instrumental activities of daily living (ADLs). It can be completed by a caregiver in questionnaire format, or administered by a clinician/researcher as a structured interview with a caregiver.

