9.3 STATISTICAL ANALYSES

9.3.1 GENERAL APPROACH

Categorical and continuous demographic and clinical data will be compared between groups with the Fisher's exact or non-parametric Kolmogorov-Smirnov tests. Biomarker data will be inspected for normality with the Shapiro-Wilk test. Associations between clinical and biomarker data will be analyzed with Spearman correlations. Given the exploratory nature of the study, correlations will not be corrected for multiple comparisons and only uncorrected results are presented. Changes in clinical variables and biomarkers will be determined by calculating a change score as the ratio of value at week 16 over the value at baseline. Thus, a change score of 1 will signify no change compared to baseline and change scores < 1 and > 1 reflect, respectively, a decrease or an increase in the neurocognitive or functional scale score or biomarker concentration at week 16, compared to baseline. Between-group change scores will be compared with the non-parametric Kolmogorov-Smirnov tests.

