9.3.3 ANALYSIS OF THE SECONDARY ENDPOINT(S)

Kolmogorov-Smirnov tests will be used to compare clinical and biomarker change scores in the two groups. Associations between clinical and biomarker data will be analyzed with Spearman correlations.

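### Section 9.3.1 defines change in the clinical scales as week 16 divided by baseline with no rule for a zero baseline, so NPI change can be undefined for an eligible patient

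*Combined protocol and SAP*

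**What the plan says.** Section 9.3.1 sets one rule. It opens with "Changes in clinical variables and biomarkers will be determined by" and continues with "calculating a change score as the ratio of value at week 16 over the value at baseline". A value of 1 means no change. Values below or above 1 mean "a decrease or an increase in the neurocognitive or functional scale score or biomarker concentration at week 16", so the rule is plainly meant for the clinical scales and not only for concentrations. Section 9.3.3 then states: "Kolmogorov-Smirnov tests will be used to compare clinical and biomarker change scores in the two groups".

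Section 8.1 describes the scales. Of ADAS-cog it says "The test is scored in terms of errors, with higher scores reflecting poorer performance", and it gives the range: "Scores can range from 0 (best) to 70 (worse"). It calls the NPI a "multi-item instrument to assess psychopathology in AD" and gives no scoring range for it.

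Section 5.1 admits prodromal as well as mild-to-moderate disease and asks patients to "Have a MMSE score between 14 and 30". Neither 5.1 nor 5.2 requires behavioral symptoms or a minimum ADAS-cog score at entry. Section 9.1 includes the NPI in the secondary hypotheses. ADAS-cog is the only clinical scale named in the secondary endpoint lists of 1.1 and section 3.

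**The concern.** A ratio to baseline suits a concentration that is always above zero. It suits a scale poorly when the best score is 0 and points are added for symptoms or errors, because the denominator can be zero or close to it.

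For the NPI, the formula can fail outright in a patient the protocol allows in. Section 9.3.1 provides no added constant, alternative score or baseline-adjusted model for that case. Someone would have to decide after the data are in whether to drop, impute or rank the patient, in arms of 7 or 8. The plan's own aim suffers too: 9.2 says the trial exists to yield effect sizes for each hypothesis, and a set of ratios containing an undefined value has no mean or SD.

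For ADAS-cog, the formula nearly always works, but the same number of points counts for more in a mild patient than in a more advanced one.

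**Working it through.** The plan gives no figure on this point to reproduce. The detectable difference in 9.2 plays no part in the check.

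**Inputs**
- Change score = week 16 / baseline (9.3.1).
- ADAS-cog runs from 0 to 70, with 0 best (8.1).
- Number randomized: 16, as 8 per arm (9.2), or 14 (synopsis, 1.1). Both are carried through.
- Assumption: no symptoms scores 0 on the NPI.
- Assumption: the share p of patients with a baseline NPI of 0 is 5%, 10% or 20%. The documents give no NPI distribution, so these values only span a range.

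**Step 1. What the formula gives for the NPI**
- 0 to 0: 0/0, indeterminate, although 9.3.1 says that no change equals 1.
- 0 to 6: 6/0, no finite value.
- 1 to 0: 0/1 = 0. 40 to 0: 0/40 = 0. Every patient who starts above 0 and ends at 0 scores exactly 0, whatever the size of the fall.

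**Step 2. How likely a zero baseline is**

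P(at least one) = 1 − (1 − p)^n; expected number = n × p.

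| p | n = 16: chance | expected | n = 14: chance | expected |
|---|---|---|---|---|
| 5% | 1 − 0.95^16 = 56% | 0.8 | 1 − 0.95^14 = 51% | 0.7 |
| 10% | 1 − 0.90^16 = 81% | 1.6 | 1 − 0.90^14 = 77% | 1.4 |
| 20% | 1 − 0.80^16 = 97% | 3.2 | 1 − 0.80^14 = 96% | 2.8 |

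**Step 3. ADAS-cog: the same change at different baselines**
- 4 points worse: 12/8 = 1.50 from a baseline of 8; 34/30 = 1.13 from a baseline of 30.
- 3 points worse or better: 9/6 = 1.50 or 3/6 = 0.50 from 6; 33/30 = 1.10 or 27/30 = 0.90 from 30. The distance from 1 is 0.50 against 0.10, five times as large, in both directions.
- Order can reverse: 8 to 12 (1.50) ranks as worse than 30 to 40 (40/30 = 1.33), although the second patient lost 10 points and the first 4.

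**Step 4. How much this matters for ADAS-cog**

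This is an illustration with assumed inputs: baseline uniform from 6 to 40, change SD 4.
- Rank correlation of the ratio with the point difference is 0.97 when there is no mean change and 0.88 with a 4-point mean shift. With baseline it is 0.00 and −0.37 respectively.
- Kolmogorov-Smirnov power with 8 per arm, difference against ratio: 23% against 22% for a 4-point effect, 53% against 49% for 6 points, 79% against 74% for 8 points.

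**The case against.** The strongest reply is that the tests are nonparametric. A patient who goes from 0 to 6 could be placed at the top rank and kept, and 0 to 0 could be set to 1 because 9.3.1 gives 1 the meaning of no change. Both are workable conventions, but neither is written down, and neither restores a mean, SD or effect size.

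A reader might infer that the plan drops patients with no baseline symptoms, including those who develop symptoms on treatment. The text does not say so. It is silent on undefined scores, and exclusion is only one of the things an analyst might do.

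A reader might also infer that the ADAS-cog ordering reflects baseline stage as much as change, or that the ratio biases the comparison between arms. Step 4 does not support the first: under those assumptions change dominates the ordering, and baseline enters only when there is a mean shift. Nor do the documents show the second. Allocation is randomized 1:1, and a low baseline magnifies improvement and worsening alike. Proportional change is a legitimate, if less usual, measure.

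Two limits on the concern stand. The documents give a minimum of 0 for ADAS-cog but not for the NPI. And eligibility permits mild patients without showing how many will enter, so low ADAS-cog baselines may occur rather than will.

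**Conclusion.** The rule as written is faulty for the NPI, and the gap is more than missing detail: a patient who meets every entry criterion can have a change score that the formula cannot produce. This rests on the assumption that no symptoms scores 0. The chance that it happens at least once is 51% to 97% over the assumed zero rates and the two stated sample sizes; the true rate is unknown.

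For ADAS-cog the fault is milder. The ratio gives extra weight to changes at low baselines, so the ordering partly reflects disease stage, at a small illustrative cost in power (1 to 5 percentage points). The zero-baseline fault is the main reason to act.

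This should be fixed, but a reader might take it as a threat to the trial's main result, and it is not. The primary endpoint is adverse events and is untouched. The NPI is in the hypotheses but in neither list of secondary endpoints. For biomarker concentrations above zero the ratio is workable.

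**What to change.** In 9.3.1, define change for the NPI and ADAS-cog as the post-treatment score minus the baseline score. Apply the same definition to CTT and ADCS-ADL for consistency; no separate fault is shown for those two. Identify the post-treatment score as the one taken after 16 weeks of treatment, which is the week-19 visit in the schedule of activities because that table counts weeks from screening and treatment runs over weeks 3 to 18. State the direction of improvement for each scale; for ADAS-cog, lower is better, as 8.1 implies. Keep the ratio, or its logarithm, for biomarker concentrations only. Settle this before unblinded data are seen.

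A baseline of 0 then gives a defined score, and a 3-point change counts as 3 points at every baseline.

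The cost is about one sentence, with no new data, visits or patients. The one downside is that clinical and biomarker changes no longer share a common scale. The planned Spearman correlations do not need one.

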3 OBJECTIVES AND ENDPOINTS

The primary objective of the study is to assess the safety and tolerability of home transcranial photobiomodulation (tPBM) treatments delivered with a commercially available PBM device (i.e., the Vielight Neuro Gamma device). The primary endpoint will be all adverse events.

The secondary objects of the study are to examine the effects of home tPBM on cognition, behavior, and fluid biomarkers of AD in patients with biomarker confirmed diagnoses of mild-to-moderate AD. Secondary endpoints will be change in the Alzheimer's Disease Assessment Scale, Cognitive Subscale (ADAS-cog), and change in fluid biomarkers of AD (e.g., A β 40, A β 42, total and phosphorylated tau, neurofilament light chain).

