9.2 SAMPLE SIZE DETERMINATION

The purpose of the proposed study is to gather the data required so that effect size estimates may be calculated for each of the study hypotheses. Moreover, there are no published human studies on the effects of tPBM on levels of these biomarkers. Therefore, one of the goals of this study is to obtain a reliable effect size estimate of tPBM on brain function and fluid biomarkers of neurodegeneration, inflammation, and neurotropic factors in anticipation of a larger PBM dementia trial. Power analyses suggest that based on our proposed sample size (8 randomly assigned to tPBM and 8 to sham), at power = .80 and alpha = .05, we will be able to detect evidence of meaningful between-group differences (≥ 0.25 SDs) in the behavioral and biomarker outcome measures.

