9.3.2 ANALYSIS OF THE PRIMARY ENDPOINT(S)

Safety and AEs will be assessed at each in-person study visit and during bi-monthly check-ins. We will use Kolmogorov-Smirnov test to compare the number of AEs in each group. To examine tolerability, we will determine the total number of treatment days and average treatment days per week in each group.

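### Effect-size estimation is a stated purpose, but section 9.3 names no signed between-arm effect or confidence interval, only the Kolmogorov-Smirnov test

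*Combined protocol and SAP*

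**What the plan says.** Section 9.2 sets the purpose as to "gather the data required so that effect size estimates may be calculated for each of the study hypotheses" and adds that "one of the goals of this study is to obtain a reliable effect size estimate of tPBM on brain function and fluid biomarkers", with a larger trial in view. Section 9.1 hypothesises better cognition and behaviour, and lower neurofilament light chain, on active treatment than on sham.

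The analysis text is short. Section 9.3.1 defines change by "calculating a change score as the ratio of value at week 16 over the value at baseline" and continues: "Between-group change scores will be compared with the non-parametric Kolmogorov-Smirnov tests". Section 9.3.3 repeats it for the secondary endpoints: "Kolmogorov-Smirnov tests will be used to compare clinical and biomarker change scores in the two groups". Section 3 states that "The primary endpoint will be all adverse events", and 9.3.2 analyses it thus: "We will use Kolmogorov-Smirnov test to compare the number of AEs in each group".

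The other methods named do not estimate a treatment effect. Fisher's exact test is for categorical demographic and clinical data, Spearman correlation is for associations, and tolerability is summarised as treatment days within each arm. Sidedness and the method for KS p-values are not given.

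Arm size is "8 randomly assigned to tPBM and 8 to sham" in 9.2. The synopsis total of 14, at the 1:1 ratio in 6.3, implies 7 per arm. Both are used below.

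**The concern.** A trial meant to inform a larger one should fix in advance what number it will hand over: which contrast, on which scale, with what uncertainty. A two-sample KS test supplies none of these. It reports the largest gap between two distribution functions, and in its usual two-sided form it does not say which arm did better.

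The only analysis scale in 9.3 is the raw ratio to baseline. That is awkward for planning. Ratios are skewed, and on a clinical scale the same point change gives a different ratio at each baseline level.

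Leaving estimand, scale and interval open until the data are seen, with 14 to 16 patients and many endpoints, also leaves room for selective choice.

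For the primary endpoint, the risk is that a non-significant KS comparison of AE counts is read as reassurance about safety.

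**Working it through.** **The plan's own figure.** Section 9.2 claims 80% power at alpha .05 for differences of 0.25 SD or more with 8 per arm. A two-sided two-sample t test has noncentrality 0.25 × √(8/2) = 0.5 and power 7.5%, so the figure does not reproduce. That is a separate problem, and nothing below depends on it.

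**Is an estimator named?** Reading 9.3.1 to 9.3.6 in order: ratio change score; KS for change scores; KS for AE counts; treatment days by arm; Fisher and KS for baseline comparisons; no interim analysis; exploratory biomarker effects and correlations with no method of estimation. No difference, ratio, shift, standardised effect, risk difference or interval appears.

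**True size of the exact KS test, equal arms.** P(D ≥ k/n) = 2 Σ (−1)^(j+1) C(2n, n−jk) / C(2n, n), summed over j ≥ 1. Only j = 1 contributes here.
- n = 7: k = 5 gives 2 × 91/3432 = 0.0530; k = 6 gives 2 × 14/3432 = 0.0082.
- n = 8: k = 5 gives 2 × 560/12870 = 0.0870; k = 6 gives 2 × 120/12870 = 0.0186.

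The test therefore rejects only at D ≥ 6/7 or 6/8. Exact Mann-Whitney rejects at U ≤ 8 (size 3.79%) or U ≤ 13 (4.99%).

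**Power for a 1 SD shift, exact p-values.** Simulated, data scaled to SD 1; each power cell is KS / Mann-Whitney.

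| Arms | KS size | MW size | Normal | Laplace |
|---|---|---|---|---|
| 7 vs 7 | 0.82% | 3.79% | 12% / 34% | 23% / 44% |
| 8 vs 8 | 1.86% | 4.99% | 23% / 44% | 39% / 54% |
| 7 vs 8 | 3.3% | 4.0% | 29% / 37% | 45% / 47% |
| 6 vs 7 | 3.8% | 3.5% | 26% / 30% | 39% / 39% |

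**P-value method.** At 8 vs 8, D = 5/8 gives p = 0.087 exact, 0.088 from the uncorrected limit, 0.0497 with the Stephens correction and 0.0493 from one common software asymptotic formula. The last two reject, at a true size of 8.7%. At 7 vs 7 the same two methods reject at D = 5/7, at a true size of 5.3%.

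**AE counts.** The documents give no expected rate for this trial, so Poisson means per participant are assumed. Each cell is power of KS with its standard exact p-value / exact rank test with ties (approximate; simulation error up to about 1 point).

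| Doubling | 7 vs 7 | 8 vs 8 | 7 vs 8 |
|---|---|---|---|
| 0.5 to 1 | 1% / 9% | 3% / 12% | 4% / 12–14% |
| 1 to 2 | 3% / 23% | 7% / 28% | 9–10% / 25–29% |
| 3 to 6 | 20% / 64% | 36% / 72% | 42–43% / 68–69% |

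Ranges at 7 vs 8 reflect repeat runs and which arm is larger. A permutation KS that allows for ties narrows the gap without closing it: 14% and 44% (7 vs 7), 16% and 43% (8 vs 8), for the last two rows.

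**Precision to expect.** The half-width of a 95% t interval for a mean difference is t(0.975, 2n−2) × √(2/n) SD.
- 8 vs 8: 2.145 × 0.500 = 1.07 SD.
- 7 vs 7: 2.179 × 0.535 = 1.16 SD.

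**The case against.** The strongest reply is that KS is a valid test, the trial is an exploratory pilot, and effects can be computed from the data whatever test is named. All three are true. They do not answer the main point, because 9.2 makes estimation the purpose and 9.3 fixes no estimate. The reference in 9.2 to differences in SDs hints at a standardised difference and narrows the gap a little, but 9.3 does not turn it into an estimator.

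A reader might infer that KS always loses badly to a rank test. That is not supported. The large deficit comes mostly from coarse p-values at exactly equal arms. One missing participant cuts it to 8 points or fewer, and with Laplace data it can vanish. Losses are plausible, since section 7 provides for withdrawals and eligibility requires agreement to a second lumbar puncture. Some asymptotic p-values also remove the deficit, at the price of the inflated sizes shown above.

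A reader might also assume high AE rates from the broad definition in 8.3.1. Section 2.2.1 points the other way: it reports no AEs in the investigators' earlier study of this device, or in a study of a similar one. At 0.5 vs 1 neither test is useful.

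Two smaller inferences should be avoided. Fisher's test in 9.3.1 is not confined to baseline data. And although the ADAS-cog range formally allows a zero baseline, where the ratio is undefined, nothing suggests this will occur in symptomatic patients.

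**Conclusion.** The concern holds as a gap between purpose and analysis: no signed between-arm effect and no interval is prespecified for any endpoint. This follows from the text alone, whatever the arm size.

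The inefficiency of KS is secondary and conditional. For a 1 SD shift it costs 15 to 22 points of power at exactly equal arms with exact p-values, but between 0 and 8 points at 7 vs 8 or 6 vs 7. For AE counts the deficit persists with unequal arms under the assumed Poisson doublings, but those rates are assumptions and may be too high.

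The documents do not support calling KS invalid, or saying that effects cannot be obtained from the data. The point should be fixed before analysis; it does not prevent the trial from running.

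**What to change.** - **Sections 9.3.1 and 9.3.3.** Make the main result for each endpoint a signed between-arm effect with a 95% CI, for example the Hodges-Lehmann shift or a mean difference, and give each arm's mean and SD. Use the log of the ratio to baseline for biomarkers and the simple difference from baseline for clinical scales. Accompany it with a two-sided exact Wilcoxon/Mann-Whitney or permutation test.
- **Section 9.3.2.** Report by arm the number and proportion of participants with at least one AE, at least one device-related AE and at least one SAE, with exact 95% CIs. If counts are compared, use an exact test that handles ties. State that a non-significant comparison is not evidence of safety.
- **If KS is kept.** Label it supportive and specify exact p-values.

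The cost is SAP wording and a few lines of code on data already planned, with no change to visits or sample size. The downsides are real. Intervals will be wide, a rank test can miss a pure difference in spread that KS might detect, clinical scales move from the planned ratio to a difference, and AE power stays limited with any test at this size.

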9.3.2 ANALYSIS OF THE PRIMARY ENDPOINT(S)

Safety and AEs will be assessed at each in-person study visit and during bi-monthly check-ins. We will use Kolmogorov-Smirnov test to compare the number of AEs in each group. To examine tolerability, we will determine the total number of treatment days and average treatment days per week in each group.

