1 PROTOCOL SUMMARY

1.1 SYNOPSIS

Title:	Examining the Impact of Photobiomodulation on Cognition, Behavior, and Biomarkers of Alzheimer’s Disease.
Study Description:	The proposed sham-controlled pilot trial will investigate the safety and tolerability of 16 weeks of home transcranial photobiomodulation (tPBM) treatment with commercially available device (i.e., Vielight Neuro Gamma) in 14 patients with mild-to-moderate Alzheimer’s Disease (AD). We will also examine the effects of home PBM on the cognitive function, behavioral symptoms, cerebrospinal fluid and blood biomarkers of AD pathology, including amyloid burden, tangle pathology, axonal injury, microglia activation/inflammation, and neurotrophic factors. We hypothesize that home PBM treatments will be safe and tolerable. We further hypothesize that effect sizes will suggest AD patients randomized to the active PBM condition have improved cognitive function and fewer behavioral symptoms after 16 weeks compared to patients randomized to Sham. Based on reports that PBM upregulates neuroprotective factors, reduces neuroinflammation, induces peripheral and central nerve regeneration, and prevents degeneration, we hypothesize that these behavioral improvements will correlate with changes in fluid biomarkers of neurodegeneration (i.e., neurofilament light chain, NfL) and Alzheimer’s disease (e.g., A β 42 and A β 42/A β 40, total- and phosphorylated-tau).
Objectives:	Primary Objective: Examine the safety and tolerability of home tPBM delivered with a commercially available PBM device. Secondary Objectives: Examine the effects of home tPBM on cognition, behavior, and fluid biomarkers of AD.
Endpoints:	Primary: All adverse events Secondary: Change in ADAS-cog and biochemical biomarkers (A β 40, A β 42, total and phosphorylated tau, NfL)
Study Population:	Men and women, ages 50 years or older with have prodromal, mild or moderate typical or atypical AD, supported by clinical AD biomarkers and a Mini-Metal State Exam (MMSE) score > 13.
Phase or Stage:	1B
Description of Sites/Facilities Enrolling Participants:	San Francisco VA Medical Center and University of California Memory and Aging Center
Description of Study Intervention/Experimental Manipulation:	Transcranial and intranasal photobiomodulation, delivers near-infrared light ($\lambda = 810 \text{ nm}$, 40 Hz, 40-150 mW/cm ²) to the scalp and one nostril.
Study Duration:	36 months
Participant Duration:	4-8 months

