The risks to the patient and operator are no greater than for other LED-based therapies that are intended for use without clinical supervision. The device is intended as an adjunct to current pharmacological therapies and is not intended to replace those therapies; therefore, lack of efficacy does not pose a significant risk in the context of this clinical trial. During the clinical trial, patients will be proactively assessed for adverse effects on an ongoing basis. The risks associated with the use of the Vielight Neuro Gamma device are equivalent to those for other low-level light therapy class II devices.

There were no significant or any adverse events in the PI's other study involving the Vielight Neuro Gamma device ([name], 2019). However, one study partner, who do not have dementia, reported feeling "tired" after he tried using the Vielight Gamma device for 20 minutes. There were also no significant or any adverse events reported in the Saltmarche et al. (2017) study, which used the similar Vielight Neuro Alpha device in elderly patients with dementia

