8.3 ADVERSE EVENTS AND SERIOUS ADVERSE EVENTS

8.3.1 DEFINITION OF ADVERSE EVENTS

An **adverse event** (AE) is any symptom, sign, illness, or experience that develops or worsens in severity during the study. Intercurrent illnesses or injuries should be regarded as adverse events. Abnormal results of diagnostic procedures are adverse events if the abnormality:

- results in study withdrawal
- is associated with a serious adverse event
- is associated with clinical signs or symptoms
- leads to additional treatment or to further diagnostic tests
- is considered by the investigator to be of clinical significance

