8.3.3.2 RELATIONSHIP TO STUDY INTERVENTION/EXPERIMENTAL MANIPULATION

Each adverse event will be judged by the Investigator as to its relationship and level of relatedness to the investigational device. Relatedness will be scored consistent with CTCAE v4.0 guidelines:

- Unrelated – the AE is clearly not related to the investigational agent(s),
- Unlikely – the AE is doubtfully related to the investigational agent(s),
- Possible – the AE may be related to the investigational agent(s),
- Probable – the AE is likely related to the investigational agent(s),
- Definite – the AE is clearly related to the investigational agent(s).

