9 STATISTICAL CONSIDERATIONS

9.1 STATISTICAL HYPOTHESES

- Primary Endpoint:

We hypothesize home transcranial photobiomodulation (tPBM) treatments delivered with the NeuroGamma device will be safe and that patients with mild-to-moderate AD will find home tPBM treatments tolerable.

- Secondary Endpoint(s):

We hypothesize that AD patients randomized to active tPBM have improved cognitive function (i.e., performance on the ADAS-cog, and CTT) and behavioral symptoms (i.e., NPI and ADCS-ADL) after 16 weeks compared to patients in the Sham group.

We hypothesize that AD patients randomized to active tPBM have decreased levels of NfL after 16 weeks compared to patients in the Sham group.

In exploratory analyses, we will examine the effects of 16 weeks of PBM on fluid levels of A β 42 and A β 42/A β 40, total- and p-tau. We will also explore the relationship between changes in cognition and behavior with changes in fluid biomarkers.

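### The primary endpoint (all AEs) is analysed only by a Kolmogorov-Smirnov test: no AE incidence, between-arm estimate or interval is planned, and the test is a weak choice for small tied counts

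*Combined protocol and SAP*

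**What the plan says.** Section 3 makes all adverse events the primary endpoint. The hypothesis in Section 9.1 is that home treatment "will be safe and that patients with mild-to-moderate AD will find home tPBM treatments tolerable". Section 9.2 gives the purpose of the study as collecting data so that "effect size estimates may be calculated for each of the study hypotheses".

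Section 9.3.2 then specifies one AE analysis: "We will use Kolmogorov-Smirnov test to compare the number of AEs in each group". Its only other planned summary is of treatment days, which measures exposure and tolerability rather than AEs. Sections 9.3.1 and 9.3.4 assign Fisher's exact test to demographic and clinical data, and nothing assigns it to AEs. Seriousness, severity, expectedness and relatedness are classified for each AE (Section 10.1.4), but no summary by arm is specified.

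Section 9.2 has "8 randomly assigned to tPBM and 8 to sham", while the synopsis plans the trial "in 14 patients with mild-to-moderate" disease, which is 7 per arm at 1:1.

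The documents give no expected AE rate. The AE definition in Section 8.3.1 is broad: "any symptom, sign, illness, or experience that develops or worsens in severity during the study". Against that, Section 2.2.1 says "There were no significant or any adverse events in the" earlier study of this device. The same section also cites a 16-session trial with more mild side effects on active treatment.

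**The concern.** A KS test gives a p-value and a maximum distance between two distributions. It does not say how many participants had an AE, how far the arms differ, or how high an incidence the data leave open. For a pilot of 14 to 16 people those are the useful safety results, and Section 9.2 says estimates are what the study is for.

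The test also suits the data poorly. Standard KS critical values assume continuous data, whereas AEs per participant are small integers with many ties, and the plan does not state how ties are handled. If AEs are not rare, the planned test gives up sensitivity that a simple alternative would keep.

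**Working it through.** **Reading.** I take the quantity tested to be AEs per participant. A two-sample KS test cannot be run on one total per arm.

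**The plan's own figure.** There is none for AEs. The power statement in Section 9.2 covers behavioural and biomarker measures only, so there is nothing to reproduce here.

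**Cut-off without ties.** For n per arm, P(D ≥ k/n) = 2 Σⱼ (−1)^(j−1) C(2n, n−jk) / C(2n, n), summed over j = 1, 2, …

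- n = 8, k = 5: 2 × 560 / 12,870 = 0.087
- n = 8, k = 6: 2 × 120 / 12,870 = 0.0186
- n = 7, k = 5: 2 × 91 / 3,432 = 0.053
- n = 7, k = 6: 2 × 14 / 3,432 = 0.0082

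In both cases rejection at two-sided 5% needs k = 6, so the size is already 1.9% (n = 8) or 0.8% (n = 7) before ties.

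**Effect of tie handling.** Suppose 5 of 8 participants on one arm have one AE each and none of 8 on the other. The standard two-sided exact KS p is 0.087. Conditioning on the observed ties gives 2 × C(8,5) / C(16,5) = 2 × 56 / 4,368 = 0.026.

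**Size on assumed counts.** Simulation with 8 per arm, nominal two-sided 5%, equal arms, and means from 0.5 to 5 (Poisson, or negative binomial with variance μ + μ²):

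- standard KS (ties ignored): 0.25% to 1.2%
- tie-respecting permutation KS: 1.4% to 2.8%
- exact permutation rank-sum: 1.6% to 4.7%

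**Power for a doubling of Poisson counts:**

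| Sham mean | Standard KS, n = 8 | Tie-respecting KS, n = 8 | Rank-sum, n = 8 | Standard KS, n = 7 | Rank-sum, n = 7 |
|---|---|---|---|---|---|
| 0.25 | 0.9% | 3.6% | 4.0% | 0.4% | 2.3% |
| 0.5 | 2.9% | 9.1% | 11.6% | 1.2% | 8.9% |
| 1 | 6.9% | 15.7% | 27.7% | 3.0% | 22.4% |
| 2 | 20.5% | 31.5% | 53.2% | 10.3% | 45.2% |
| 5 | 64.3% | 67.8% | 91.1% | 42.3% | 85.7% |

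At n = 8 and sham means 1, 2 and 5, standard KS costs about 21, 33 and 27 points against rank-sum. The remaining 72%, 47% and 9% of doublings missed are due to sample size, not to the test.

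**Clustered counts.** With negative binomial counts, variance μ + φμ², φ from 0.5 to 1, n = 8 and doubling from means 1, 2 and 5:

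- standard KS: 2.5–3.7%, 4.0–7.0%, 6.4–11.9%
- rank-sum: 11.8–17.0%, 15.4–24.2%, 17.4–29.9%

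**What an interval would show.** The exact two-sided 95% upper limit for 0 of n is 1 − 0.025^(1/n): 1 − 0.025^(1/8) = 36.9%, and 1 − 0.025^(1/7) = 41.0%. One event in 8 gives 0.3% to 52.7%.

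**Why incidence alone is not enough.** Under Poisson counts the chance of at least one AE is 1 − exp(−μ). At means 2 v 4 that is 86% v 98%, so a doubling of events nearly disappears. Counts are needed beside incidence.

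**The case against.** The strongest reply is that choosing between KS and rank-sum in a phase 1B pilot of this size is a choice between weak tests. The plan claims no power for AEs, the only AE evidence for this device is of none, and the alternatives simulated are all shifts in mean count, which suit rank-sum. Much of this stands. At sham means of 0.5 or less, or with clustered counts, neither test is useful, and the test is the lesser part of the point. But more AEs on active treatment is the safety question, and rank-sum was the more sensitive test in every scenario. The reply also leaves the missing estimates untouched.

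Several stronger readings are tempting, and the documents or figures do not support them:

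- A reader might infer that the plan treats a non-significant result as proof of safety. It never says so.
- A reader might quote a single KS size, such as 0.5%, as a property of the plan. It depends on an assumed AE rate and on ignoring ties, and the plan specifies neither.
- A reader might infer that significance turns on trivial software options. In the 5/8 v 0/8 example the default exact two-sided calculation gives 0.087 and the classical large-sample formula 0.088. Only a non-default approximation (0.049) or a one-sided test (0.044) falls below 0.05. The real ambiguity is tie handling (0.087 v 0.026).
- A reader might infer that Fisher's exact test on any AE is always worse than KS. It is worse for this doubling at sham means 1, 2 and 5 (5.6%, 0.2%, 0.0%), but better than standard KS at 0.25 and 0.5 (3.8% and 8.9%).

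**Conclusion.** The point holds in two parts of unequal weight. First, and free of any assumption about AE rates, the primary endpoint has no planned incidence, between-arm estimate or interval, which does not meet the purpose set in Section 9.2. Without them, a result as favourable as no AEs in an arm would be reported with no indication that an incidence near 40% remains possible.

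Second, KS is an inefficient test for these data. The stated sizes and losses rest on assumed Poisson or negative binomial counts, two-sided 5% and 8 per arm. With 7 per arm standard KS is weaker still. Respecting ties narrows the gap to rank-sum but does not close it. This is not a claim that a better test would make the trial adequate for detecting harm.

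**What to change.** Amend Section 9.3.2 before unblinding, along these lines:

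> AEs with onset from randomization to the week 19 visit will be summarised by randomized arm; AEs in the open-label phase will be reported separately. For each arm, the number and percent of participants with any AE, any SAE, any AE judged possibly, probably or definitely related to the device, and withdrawal due to an AE will be given with exact (Clopper-Pearson) 95% CIs. AEs per participant will be summarised by arm. Between-arm differences in incidence and in mean count will be given with 95% CIs. A non-significant difference will not be taken as evidence of safety.

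The methods for the two between-arm intervals should be named in advance.

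If a test of counts is kept, replace KS with a two-sided exact permutation rank-sum test using midranks for ties. Fisher's exact test is suitable for rare categories such as SAEs.

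The window needs stating for two reasons. The schedule of activities collects AEs through the optional open-label active phase, so sham participants' events on active treatment could otherwise be counted as sham. Also, Section 8.3.4 records events from consent, while Section 8.3.5 logs only those after randomization. The 14 and 16 participant totals should be reconciled at the same time, because they set the denominators.

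The cost is wording and a few extra tables. The AE classifications are already collected; the one addition is to note when a withdrawal is due to an AE. The intervals will be wide and the safety conclusion more cautious.
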